### *Secondary objectives*

1. To determine the course of the histological findings in the two treatment groups.
2. To determine the course of the balance in the subpopulations of lymphocytes (CXCR3highCD4+/CCR4highCD4+) and regulatory cells (Treg CCR4high) using flow cytometry in samples from peripheral blood and FNAP after withdrawal of steroids in the third month post-transplant versus conventional triple immunosuppression.
3. To analyze and compare the incidence of immunological dysfunction in the two treatment arms, as well as graft and patient survival at one and two years of follow-up.
4. To examine the potential metabolic and cardiovascular benefit of steroid withdrawal in terms of renal function, hypertension, diabetes and hyperlipidemia.
5. To assess the adherence to treatment with immunosuppressors in the two treatment groups and its impact on the generation of DSA.

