**Selection procedure and coding:** Once written informed consent was obtained at the screening visit, the baseline data were collected to determine the eligibility of the patients to participate in the study. Those patients who fulfilled the inclusion criteria were randomized in a proportion 1:1 to one of the two treatment arms.

Randomization was done locally at each center via the case report form (CRF) to assign the eligible patients to one of the two treatment arms. This randomization was done using a computer program after introducing the patient data into the electronic database (CRF) and determining the

status of the anti-HLA antibodies (DSA) and the histological findings at the third month post-transplant.

**Description of the treatment groups:** After verifying the inclusion/exclusion criteria, the patients were distributed randomly in the two study groups:

**Group A:** steroids, tacrolimus (prolonged-release –Advagraf, or immediate-release tacrolimus – generic or Prograf, according to their availability in each Community) plus MMF or MPA.

**Group B:** tacrolimus (prolonged-release –Advagraf, or immediate-release tacrolimus –generic or Prograf, according to their availability in each Community) plus MMF or MPA.

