**Treatment schedule:**

**Group A: Tacrolimus** 0.15 mg/Kg/day to maintain levels of 8-12 ng/ml for the first two months.

With effect from the third month tacrolimus 0.1 mg/kg/day to maintain levels of 5-8 ng/ml;

**Mycophenolate mofetil (MMF)** 2 gr/day or mycophenolic acid (MPA) 1440 mg/day for the first two weeks post-transplant. With effect from this point MMF 1-1.5 gr/day or MPA 720-900 mg/day; **Steroids:** 0.5 gr of methyl prednisolone intraoperatively and 125 mg on day 1; prednisone 30 mg for the first two weeks post-transplant, then tapering 5 mg/week to reach the dose of 5 mg/day at the second month post-transplant. After this the same dose of prednisone was continued.

This treatment was maintained throughout the whole study period in Group A.

**Group B:** These patients received the same treatment schedule as those of Group A up to the time of randomization (third month post-transplant). After this they received: **Tacrolimus** 0.1 mg/kg/day to maintain levels of 5-8 ng/ml; **MMF** 1-1.5 g/day or **MPA** 720-900 mg/day; withdrawal of steroids between the third and fourth month post-transplant as per usual practice in the center.

Both treatment groups received pre-operatively tacrolimus 0.12 mg/Kg orally and MMF 1 g. or MPA 720 mg. Both treatment groups could receive induction therapy with anti-CD25 monoclonal antibodies (Basiliximab 20 mg iv on days 0 and 4) or polyclonal antibodies (Thymoglobulin 1 mg/kg/day for 4-7 days) in patients at risk of delayed graft function and delayed introduction of tacrolimus.

**Other treatments:** Cases of acute rejection were treated with 3 boluses of 500 mg/day of i.v. methylprednisolone. Cases of steroid-resistant rejection were treated with a standard cycle of 7-10 days of rabbit thymoglobulin. Cases of acute humoral rejection were treated in accordance with the protocol at each center: plasmapheresis, immunoglobulins, and rituximab, either alone or in combination.

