### **Variables:**

#### *Efficacy variables:*

The *primary variable* was the presence of donor-specific anti-HLA antibodies (DSA) at 24 months.

The *secondary variables* were:

- a) Graft and patient survival.
- b) Rate of acute clinical rejection, confirmed by biopsy, calculated glomerular filtration rate (determined by aMDRD) and proteinuria at 3, 6, 12 and 24 months.
- c) BP figures and number of hypertensive patients, lipid levels and need for lipid-lowering drugs, and increase in weight and BMI.
- d) Rate of post-transplant diabetes mellitus (PTDM) or glucose intolerance one year post-transplant according to the criteria of the ADA (PTDM: baseline glycemia  $\geq 126$ , or  $\geq 200$  mg/dl after glucose overload, or need for treatment; glucose intolerance: glycemia after overload of 140-199 mg/dL).
- e) Determination of the lymphocyte subpopulations (CXCR3highCD4+; CCR4highCD4+ and Treg CCR4high) by flow cytometry at 1, 3, 6, 12, 18 and 24 months.
- f) Appearance of acute or chronic pathological lesions of the graft using:

\*Kidney graft biopsy. Biopsies were done before randomization (month 3 post-transplant) and in month 24 post-randomization (protocol biopsies). In the case of suspected acute rejection a biopsy of the graft was done before or within 48 hours of starting anti-rejection treatment. Likewise, a graft biopsy was done at any time if graft dysfunction was detected, as evidenced by proteinuria 0.5 g/day or an increase in the serum creatinine of 25% above its baseline level. The biopsies were evaluated according to the Banff'09 classification (*Sis B, et al Am J Transplant 2010;10: 464-71*). Biopsies done for clinical indication and those done prior to randomization were evaluated locally at each participating center. The local pathologist interpreted the biopsy for the presence of clinical or subclinical rejection, borderline lesions or progression of chronic lesions that

explained a possible graft failure to thus provide the most opportune treatment. The biopsies done and the pre-randomization and final visits were also sent to the pathologist at Carlos Haya Hospital, Malaga, who also interpreted and classified them using the same Banff'09 criteria. The biopsies were processed in each center and sent to the central pathologist for study. The slides comprised at least 2-3 slices of the biopsy. The staining was done locally (hematoxylin eosin, periodic acid Schiff, Masson trichrome and methenamine silver).

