For the measurement of C4d an unstained slide was sent to the reference center, at ambient temperature.

\*The interpretation of the central pathologist was used mainly to analyze the progression of the chronic graft nephropathy. For each patient, the sum of the classification of the chronic lesion was obtained from the 5 histological categories: 1) cg: chronic glomerulopathy. 2) ci: chronic interstitial. 3) ct: tubular atrophy (chronic). 4) cv: arteriolar hyalinosis (chronic). 5) mm: mesangial matrix.

*Confounding variables:* Donor and recipient age, HLA compatibility and PRA, delayed graft function, BMI, CMV infection, concomitant treatment (statins, ACEIs/ARA, beta blockers, diuretics, and ASA), scale of treatment compliance and levels of tacrolimus or CsA.

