## **STATISTICAL ANALYSIS PLAN.**

Descriptive statistics are presented together with the various analyses. Both an intention-to-treat analysis and an analysis according to the final treatment were done. The categorical variables were analyzed using the chi-square test or Fisher's exact test, according to needs. The quantitative data were analyzed using the Student t test or the Mann-Whitney U test, according to needs. Changes over time in the DSA and lymphocyte subsets in the two study groups were analyzed using a general linear model for repeated measures, adjusting for confounding variables. Correlations between the various subsets were analyzed using Pearson correlation. The graft and patient survival curves were calculated with the Kaplan-Meier method. The rates of survival of the groups were compared with the log-rank test. Finally, a linear regression analysis was done to determine the factors associated with the generation of de novo DSA, including steroid withdrawal. The data were analyzed using SPSS 20.0.

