### **Lymphocyte subpopulations.**

A significant increase was seen in lymphocyte subpopulations in the FNAP samples compared to the peripheral venous blood samples. Likewise, the patients with borderline lesions showed an

increase in the CXCR3highCD4+ and CD14+CD16+ subpopulations in venous blood and FNAP samples compared to the patients with no subclinical inflammation in the biopsy.

Additionally, a direct correlation was found between the CD14+CD16+ subset obtained by FNAP at 3 months and the presence of IFTA at 24 months. Likewise, the CCR4highCD4+ lymphocyte subset obtained at 3 months post-transplant correlated inversely with the interstitial ( $r=-0.431$ ;  $P=0.007$ ) and tubular ( $r=-0.436$ ;  $P=0.007$ ) inflammation at 24 months post-transplant.

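### The repeated-measures model for the lymphocyte subsets names neither its visits nor its tested term, and leaves the month-3 value, the randomisation baseline, out of its covariates

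*Combined protocol and SAP*

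**What the plan says.** The statistical analysis plan gives this analysis one sentence: "Changes over time in the DSA and lymphocyte subsets in the two study groups were analyzed using a general linear model for repeated measures", with adjustment for confounding variables. No visit set, tested term or contrast follows.

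The only list of confounders is under Efficacy variables. It begins "Donor and recipient age, HLA compatibility and PRA, delayed graft function, BMI, CMV infection, concomitant treatment" and goes on to a compliance scale and drug levels. No subset value appears in it.

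Secondary objective 2 asks for the course of the subset balance "after withdrawal of steroids in the third month post-transplant versus conventional triple immunosuppression". Secondary variable (e) schedules the subsets "by flow cytometry at 1, 3, 6, 12, 18 and 24 months". The flow cytometry section instead ties them to the DSA schedule, which is pre-transplant and then months 3, 6, 12, 18 and 24. The two accounts differ only in the first sample; both include month 3.

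On timing, Selection procedure and coding places randomisation after determining the "status of the anti-HLA antibodies (DSA) and the histological findings at the third month post-transplant". The Treatment schedule says of Group B: "These patients received the same treatment schedule as those of Group A up to the time of randomization (third month post-transplant". Group B then had "withdrawal of steroids between the third and fourth month post-transplant as per usual practice in the center".

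**The concern.** Month 3 is the last scheduled measurement before the arms diverge, so it is the natural baseline for the subset comparison. If visits within a patient are correlated, using that value as a covariate removes between-patient noise from the arm differences that follow, and it needs no new sample. The plan lists other covariates but not this one.

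The silence on visits and tested term matters for the same reason. Two of the six scheduled blood samples come before any treatment difference. What the model can detect depends on whether those two enter, and on whether the arm effect or the arm-by-time term is read. At stake is power for a mechanistic secondary objective, and a reader's ability to interpret a non-significant arm comparison.

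**Working it through.** **Is month 3 available as a baseline?** Yes by schedule, on both accounts. The preliminary results also use it: a CCR4high CD4+ "lymphocyte subset obtained at 3 months post-transplant correlated inversely with the interstitial" and tubular inflammation at 24 months. So month-3 values exist for at least some patients.

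**Is there a figure to reproduce?** No. The documents give no power, effect size, SD or between-visit correlation for this analysis. What follows is an illustration.

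**Inputs**
- From the documents (Preliminary results; secondary variable e): n1 = 52, n2 = 53, so N = 105; two samples before the arms diverge and four after.
- Assumed: SD 1; arm shift d = 0.4 SD at months 6, 12, 18 and 24 and zero before; equal correlation r = 0.3 / 0.5 / 0.7; complete data; two-sided 5%.

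h = n1·n2/N = 52 × 53/105 = 26.25, and h·d² = 26.25 × 0.16 = 4.20.

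**Noncentrality (multivariate F tests)**
- Group-by-time, months 3-24: h·d² × 0.8/(1−r); df 4, N−5 = 100.
- Group-by-time, six visits: h·d² × (4/3)/(1−r); df 5, N−6 = 99.
- Joint test of the four arm differences, adjusted for month 3: h·d² × 4/[(1−r)(1+4r)]; df 4, N−6 = 99.
- The same, adjusted for both early samples: h·d² × 4(1+r)/[(1−r)(1+5r)]; df 4, N−7 = 98.

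At r = 0.5:
- 4.20 × 0.8/0.5 = 6.72
- 4.20 × 1.333/0.5 = 11.20
- 4.20 × 4/(0.5 × 3) = 11.20
- 4.20 × 4 × 1.5/(0.5 × 3.5) = 14.40

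| Test (52/53) | r = 0.3 | r = 0.5 | r = 0.7 |
|---|---|---|---|
| Group-by-time, months 3-24 | 36% | 50% | 75% |
| Joint, adjusted for month 3 | 74% | 75% | 87% |
| Group-by-time, six visits | 54% | 71% | 92% |
| Joint, adjusted for both early samples | 80% | 86% | 97% |

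Rows 1 and 2 use the same samples, as do rows 3 and 4. Allowing for estimation of the covariate slopes multiplies the adjusted noncentralities by 101/102 or 100/102 and costs at most about one point. If only months 6-24 entered the model, group-by-time would have 5% power for a constant shift, because such a shift leaves no interaction to detect.

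**Other time courses (r = 0.5, arm differences at months 6, 12, 18, 24)**

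| Course (SD) | Group-by-time, 3-24 | Group-by-time, six visits | Joint, adjusted for month 3 | Months 6-24 mean, adjusted for month 3 |
|---|---|---|---|---|
| Sustained 0.4 | 50% | 71% | 75% | 91% |
| Fading 0.8, 0.4, 0.2, 0.2 | 95% | 97% | 98% | 91% |
| Growing 0, 0.2, 0.4, 0.6 | 86% | 89% | 91% | 70% |
| Reversing 0.4, 0.4, −0.4, −0.4 | ~100% | ~100% | ~100% | 5% |

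**Correlation decaying with time** (0.5 / 0.7 / 0.85 per 6 months, sustained 0.4 SD): six-visit group-by-time 54 / 79 / 99%; joint test adjusted for month 3, 80 / 90 / over 99%. Here the first sample adds nothing once month 3 is in.

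**Smaller n.** The reported r = −0.431 with P = 0.007 implies about 38 patients if it is an ordinary Pearson test: t = 0.431 × √36/√(1−0.431²) = 2.87, P = 0.0069. The second correlation, −0.436, gives P = 0.0070 at n = 37. Those pairs also needed a 24-month histology result, so this is not the model's n. At an assumed 19/19 the four rows of the first table become 14 / 18 / 28%, 28 / 28 / 37%, 19 / 25 / 41% and 31 / 36 / 51%. The pattern is the same, with low power throughout.

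**The case against.** The strongest reply is that the plan's wording already points to a group-by-time test, which suits an objective about course. If month 3 is one of the repeated levels, that test uses each patient's month-3 value as a reference, so the baseline is not ignored. This is fair. A reader might infer that the plan discards month 3, or that its test is an arm effect diluted by averaging in pre-randomisation visits. The documents say neither. What remains is that they also do not say month 3 is a level or interaction the test. Even if both hold, group-by-time in effect subtracts the early value in full, whereas a covariate gives it the weight that the correlation supports.

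A second reply is that the advantage depends on the assumed shape. That stands against making the month 6-24 average the main test. A reader might infer from the sustained-shift row that this average always beats the plan's model, but it loses for the growing, fading and reversing courses. It also loses for a sustained shift when correlation decays slowly (97% against 99% at 0.85 per 6 months). The objection has less force against the joint test, which keeps the question of course and, at 52/53, matched or beat group-by-time over months 3-24 in every case run. Against six-visit group-by-time, though, the joint test with month 3 alone can fall slightly short: 87% against 92% at r = 0.7.

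Third, the data are collected and no affected result is visible. That is true, and it limits the severity.

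**Conclusion.** The point holds as a minor one. The visits and tested term are unstated, and an already scheduled baseline is missing from the covariates. Under a sustained 0.4 SD shift with 52/53 complete patients and equal correlation 0.3 / 0.5 / 0.7, adding month 3 gains 38 / 25 / 12 points over group-by-time on the same visits (74−36, 75−50, 87−75). With both early samples the gain over six-visit group-by-time is 26 / 15 / 5 points (80−54, 86−71, 97−92). The gain is small at high correlation. SD, correlation, effect shape and completeness are all assumptions.

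No bias follows, since randomisation protects the unadjusted comparison. The primary variable is untouched. The same sentence of the plan covers DSA over time, but absence of DSA at randomisation is an eligibility condition, so a month-3 DSA status would not vary. A reader might infer that a true arm effect on the subsets was missed. The preliminary results give no Group A versus Group B subset comparison, so the documents cannot show this.

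**What to change.** In the statistical analysis plan, for secondary objective 2, state:

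- Outcomes are the subset values at months 6, 12, 18 and 24.
- Covariates include the patient's month-3 value of the same subset, after checking that it was drawn before the first steroid reduction, plus the first scheduled sample where available.
- The test is the joint test of the arm differences at those four visits (arm plus arm-by-visit).
- Arm differences are reported by visit with confidence intervals, and the month 6-24 average is given as a summary, not as the sole main test.
- The specification was made after data collection.

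The cost is two or three sentences and one rerun of a secondary model on existing data, with no new samples. The downside is that patients without a month-3 value drop out or need imputation, so the report should give the number affected in each arm.

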## **STUDY PROTOCOL.**

### **HYPOTHESIS**

Steroids form one of the pillars of immunosuppression in transplant patients. However, their use is associated with an increase in post-transplant comorbidity. Although steroid withdrawal post-transplant can improve the metabolic and cardiovascular profile in transplant patients, it is not really known whether this therapeutic strategy results in a greater risk for the de novo appearance of donor-specific antibodies (DSA), which are associated with a reduction in kidney graft survival. Also unknown is the causal relationship between the appearance of DSA and histological lesions in stable kidney transplant patients after steroid withdrawal in the third post-transplant month. Finally, another unknown is whether this immunosuppressive strategy is associated with changes in the balance between effector and suppressor lymphocyte subpopulations that selectively infiltrate the graft via peripheral homing receptors.

This randomized controlled study of stable kidney transplant patients aimed to determine the natural history after steroid withdrawal in the third month post-transplant of the de novo production of anti-HLA antibodies (DSA), by means of the sequential measurement of DSA during the first two years post-transplant. At the same time we wished to determine the repercussion of this therapeutic strategy on the kidney graft histology by performing protocol biopsies, as well as the risk factors for the appearance of de novo DSA in these patients. Finally, we aimed to monitor sequentially the balance of the lymphocyte (CXCR3highCD4+/CCR4highCD4+) and regulatory cell (Treg CCR4high) subpopulations in peripheral blood and samples of the graft tissue obtained by fine-needle aspiration puncture (FNAP) after the withdrawal of steroids versus continuation of conventional triple therapy.

The lack of prospective serological, histological and lymphocyte subset studies in kidney transplant patients in whom steroids are withdrawn makes this study very pertinent. The findings will doubtless give rise to an immunosuppressive strategy that optimizes the results of a transplant in terms of survival.

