## STUDY DESIGN AND DURATION

This was a randomized, open-label clinical trial with two treatment arms and a follow-up of two years in patients who received a first deceased-donor kidney transplant. The combinations of immunosuppressors in the study arms were those approved in the technical documentation and used routinely in clinical practice. This was therefore a phase IV clinical trial in the usual conditions of use. The patient recruitment period was 12 months. The minimum follow-up period was 24 months.

**Inclusion criteria:** a) Both male and female patients, 18 years of age or over with no immunological risk (PRA <25% and absence of DSA) who received a first deceased or living donor kidney transplant. b) Patients who for the first three months post-transplant were receiving tacrolimus plus MPA or MMF and steroids and who had stable plasma levels of tacrolimus. c) Absence of clinical or histological immune dysfunction before randomization. d) Absence of de novo DSA at the time of randomization. e) Patients who wished and were able to give their written informed consent to participate in the study. f) Female patients who agreed to use efficient contraceptive methods during the study.

**Exclusion criteria:** a) Recipients of a multiorgan transplant. b) Retransplants. c) Presence of DSA prior to transplant or at the time of randomization. d) Cold ischemia time >30 hours. e) Patients with serum creatinine levels above 2 mg/dL or proteinuria above 1g/day at the time of randomization. f) Previous episode of severe rejection (II-B-III in the Banff/09 classification) before randomization. g) Presence of subclinical rejection in the protocol biopsy before randomization. h) Patients with BK-polyomavirus nephropathy at the time of randomization. i) Patients with recurrent or de novo glomerulonephritis. j) Patients receiving treatment with immunosuppressive drugs other than those of the clinical trial in question. k) Patients who were positive against the human immunodeficiency virus (HIV) or who had a severe systemic infection and who the investigator deems the need for continued therapy. l) Patients who had had any previous malignant disease during the previous five years, except basal cell or excised squamous cell carcinoma.

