#### **Monitoring of donor-specific anti-HLA antibodies (DSA):**

Monitoring of DSA was done with the Luminex assay and X-MAP technology. The presence of DSA was determined pre-transplant and in months 3, 6, 12, 18 and 24.

Before transplant the presence of anti-HLA antibodies was determined in all the patients by Luminex Mixed, which detects the presence of antibodies against HLA-class I and class II antigens. In positive cases the specificity of the antibodies was determined by Luminex SA (*single antigen*). Likewise, in patients with a high risk of sensitization (previous pregnancy or transfusion) the Luminex SA was also done, even if they had had a negative Luminex Mixed result. Before transplant a serum sample was taken from each patient and frozen in three aliquots of 0.5 ml in Eppendorf tubes.

If the patients had no anti-HLA antibodies pre-transplant, monitoring for these antibodies was done throughout the study using the Luminex Mixed assay. When this assay was positive for any of the measurements established in the study a Luminex SA was done to detect the specificities. If, on the other hand, a patient had a positive Luminex Mixed pre-transplant only the Luminex SA assay was done at all the successive study visits.

Any determination with a mean fluorescence intensity (MFI)  $>500$  was considered positive. All determinations of DSA were centralized at the immunology laboratory of Carlos Haya hospital, Malaga.

All the samples obtained from the various participating centers for determination of anti-HLA DSA were stored at  $-80^{\circ}$  or  $-40^{\circ}$  C until being sent. During transit the samples were stored in dry ice.

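### De novo DSA, a yes/no outcome, gets a linear risk-factor model whose standard errors can be wrong for unevenly split factors, and arm-by-time adjustment is not limited to values fixed by month 3

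*Combined protocol and SAP*

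**What the plan says.** The Hypothesis section makes it a study aim to find the consequences of steroid withdrawal, "as well as the risk factors for the appearance of de novo DSA in these patients". The Statistical Analysis Plan serves that aim with one sentence: "a linear regression analysis was done to determine the factors associated with the generation of de novo DSA, including steroid withdrawal". It does not list the candidate factors, state the outcome scale, or mention a logistic model or robust standard errors.

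Elsewhere the outcome is yes/no. The inclusion criteria require "Absence of de novo DSA at the time of randomization". The primary variable "was the presence of donor-specific anti-HLA antibodies (DSA) at 24 months". The DSA monitoring section counts a determination as positive above an MFI of 500 and adds: "The presence of DSA was determined pre-transplant and in months 3, 6, 12, 18 and 24". No section names MFI as a quantitative outcome.

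For between-group comparisons of categorical variables the plan says: "The categorical variables were analyzed using the chi-square test or Fisher's exact test, according to needs". Changes over time in DSA and lymphocyte subsets in the two groups "were analyzed using a general linear model for repeated measures, adjusting for confounding variables". The only list of such variables, under Confounding variables, mixes items fixed before randomisation (donor age, HLA compatibility, delayed graft function) with items that can change afterwards: CMV infection, co-medication, compliance, and tacrolimus or CsA levels. No time point is attached. Randomisation is at month 3.

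**The concern.** Ordinary linear regression assumes the same outcome variance at every level of a factor. For a yes/no outcome the variance is p(1−p), so it changes with risk. When a factor splits patients evenly the discrepancy nearly cancels; when the split is uneven it does not, and the precision of a real risk factor is misjudged. Which factors matter for de novo DSA is a stated aim, so the error would fall on a result that readers will look for.

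The second matter concerns the randomised contrast. Adjusting for something that the arm itself changes can remove part of the arm effect or distort it. The documents treat some listed items as things the arm may change. Secondary objective 5 compares adherence between groups and asks about its impact on DSA. Secondary variable c) includes the need for lipid-lowering drugs. The Safety assessment reports a non-significant tendency to more severe infections, CMV among them, in Group B.

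**Working it through.** The documents give no regression estimate, DSA count or planning rate, so there is no stated figure to reproduce. All DSA risks below are assumptions.

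**Inputs from Preliminary Results.** Randomised: 52 + 53 = 105. Men: 0.75 × 52 = 39 and 0.717 × 53 = 38, so 77 men and 28 women. Aged 18 to 65: 0.8269 × 52 = 43 and 0.8302 × 53 = 44, so 87, leaving 18 older. These are the only uneven patient splits at randomisation that the documents report. They serve as examples, not as known model terms.

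**Standard errors for a one-factor linear model** (smaller group n1, risk p1; larger group n0, risk p0; N = n1 + n0):
- True: √[p1(1−p1)/n1 + p0(1−p0)/n0]
- Linear model: √{[n1·p1(1−p1) + n0·p0(1−p0)]/N × (1/n1 + 1/n0)}

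For 18/87 at 20% vs 5%:
- True: √(0.16/18 + 0.0475/87) = √0.009435 = 0.0971
- Model: √[(2.88 + 4.1325)/105 × (1/18 + 1/87)] = √(0.06679 × 0.06705) = 0.0669
- Ratio: 0.0669/0.0971 = 0.69

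For 28/77 at the same risks: 0.0614/0.0796 = 0.77. For 52/53: 0.0627/0.0630 = 0.995.

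**Coverage of the nominal 95% interval.** This sums the binomial probabilities of every possible pair of event counts for which the interval contains the true difference. The SE ratio is the model SE, averaged over outcomes, divided by the true SE.

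| Split | Risks, smaller vs larger group | Coverage | SE ratio |
|---|---|---|---|
| 18/87 | 20% vs 5% | 81.5% | 0.677 |
| 18/87 | 10% vs 5% | 89.0% | 0.797 |
| 18/87 | 5% vs 20% | 99.2% | 1.450 |
| 28/77 | 20% vs 5% | 86.5% | 0.762 |
| 28/77 | 10% vs 5% | 90.3% | 0.849 |
| 28/77 | 5% vs 20% | 98.9% | 1.293 |

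**Where the problem is absent.** With no association, at a common risk of 3% to 15%, the linear test's false-positive rate is 4.1–5.7% (18/87) and 3.4–4.8% (28/77). For the 52/53 arm split, coverage is 93.9–95.4% over risk pairs from 3% to 20%.

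**Sparse counts also contribute.** Allowing unequal variances for 18/87 (same critical value) raises coverage only to 89.5% at 20% vs 5%, and lowers it from 89.0% to 84.5% at 10% vs 5%.

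**Candidate replacements.** Firth-penalised logistic regression with profile-likelihood intervals covers 95.2–97.2% over the 18/87 and 28/77 cases in both directions. In a three-term simulation (arm, sex, age band; 1,500 trials per case; 15% or 20% vs 5%, smaller group at higher risk), linear intervals cover 81.9–89.1% and Firth intervals 95.5–96.5%. HC3 robust standard errors are not a safe shortcut: with no association and 3–15% risk their false-positive rate is 7.7–25.5% (18/87) and 5.6–13.2% (28/77), because one group often has no event.

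**Covariate adjustment.** In a linear model, adding a covariate shifts the arm estimate by (arm difference in the covariate) × (its coefficient). If the arm does not affect the covariate, the expected shift is 0. For an assumed 5-point arm difference and a coefficient of 10 to 30 points, it is 0.05 × 0.10 = 0.5 to 0.05 × 0.30 = 1.5 percentage points.

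**The case against.** The strongest reply is that the harm falls on quantities the documents never show. The plan and results give percentages, means, correlations and p-values, with no confidence interval for a risk factor, and the p-value is roughly valid when a factor has no effect. That stands: a reader might infer that the linear model produces spurious risk factors, and the calculation does not support this. What remains is the misjudged precision of a real association.

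Nor is either example documented as a model term. Sex is not on the list of confounding variables, and recipient age is listed without any banding. Continuous factors were not checked. This also stands, so the figures are illustrations.

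The assumed risks may be too high. The results section says that withdrawal did not lead to DSA appearing and gives no count, whereas 20% vs 5% implies 18 × 0.20 + 87 × 0.05 = 8.0 or 28 × 0.20 + 77 × 0.05 = 9.5 events. With very few events no regression is useful, linear or otherwise. The direction rule also needs low risks: at 90% vs 60% with 18/87 it reverses (coverage 99.2%).

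The outcome might have been MFI, or linear might be a slip for logistic. The documents say neither, and in either case the text needs correcting.

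On covariates, month-3 or earlier values fit the text as well as later ones, and both arms share one tacrolimus target after month 3. A reader might infer that the arm effect has been shown to be biased; it has not. Likewise, a classical repeated-measures model drops patients with a missed visit, but no missing-visit figure is given, so no material loss can be claimed.

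**Conclusion.** The point holds within limits. The stated model does not suit the outcome as defined. For an unevenly split yes/no factor that truly affects a DSA risk below 50%, its standard error is wrong in a predictable direction. In the examples, at an assumed 20% and 5% with complete data on 105 patients, it is 24–32% too small or 29–45% too large, giving coverage of about 82–87% or about 99%. Unequal variance and sparse counts both play a part.

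A reader might conclude that the trial's main finding is undermined. It is not: the primary comparison uses chi-square or Fisher, and the steroid-withdrawal term has near-equal groups, so its interval is close to nominal even in the linear model.

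The covariate issue is a conditional risk. It arises only if values after month 3 were used and the arm affects them. Both matters concern secondary analyses and are worth fixing because the change is cheap and the risk-factor question is a declared aim.

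**What to change.** 1. Replace the linear regression with Firth-penalised logistic regression and profile-likelihood intervals, with arm plus at most two covariates fixed by month 3 (for example recipient age and HLA compatibility). Label it exploratory and post hoc, because results are already reported. With only a handful of DSA events or none, fit no model and give counts by arm with exact intervals.
2. In every arm comparison, adjust only for values fixed by month 3. Put later tacrolimus levels, compliance, CMV infection and co-medication in a separate exploratory analysis.
3. For lymphocyte subsets over time, a linear mixed model with the month-3 value as covariate is a cheap option that also keeps patients with a missed visit.
4. Report the number of patients and events for each model, and state the DSA outcome scale.

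The cost is revised wording and re-running secondary models on existing data, possibly in software other than SPSS 20.0. Intervals will be wide: an assumed 5–15% incidence gives 105 × 0.05 ≈ 5 to 105 × 0.15 ≈ 16 events, or 1.7 to 5.3 per term with three terms. With no events in Group B, the exact 95% interval for 0/53 runs from 0 to 1 − 0.025^(1/53) = 6.7%.
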